3.2. Planned Number of Patients and Regions

Approximately 65 patients are planned to be randomized to TEV-50717 versus placebo in a 2:1 ratio (approximately 43 in the TEV-50717 group; approximately 22 in the placebo group) stratified by age at baseline (6 to <12 years; 12 through 18 years) and region (US; non-US).

Details on sample size are given in Section 9.1.

This study is planned to be conducted in approximately 60 investigational centers in North America, Asia, and Europe.

3.3. Justification for Study Design and Selection of Population

Currently, there is no approved treatment available for DCP. The available treatment options address some of the manifestations of DCP, which is hyperkinetic motor impairment due to a non-progressive disturbance of brain function that occurred in the developing fetal or infant brain, generally before the age of 2 years, and will therefore have a major debilitating impact on the ability of the child with CP to further develop motor skills. Therefore, the study population will include pediatric and adolescent patients (6 through 18 years of age) with DCP with predominant choreiform movement disorder, who have had non-progressive CP symptoms since infancy (≤ 2 years of age). Diagnosis of DCP is based on the Surveillance of Cerebral Palsy in Europe criteria (Cans 2000).

Consequently, the placebo-controlled, double-blind study design (TEV-50717 versus placebo in a 2:1 ratio) was chosen for this Phase 3 study to determine whether treatment with study medication results in a statistically significant effect on dyskinetic involuntary movements of patients with DCP.

3.4. Stopping Rules for the Study

When approximately 50 patients have completed the study (including follow-up), an iDMC will perform an unblinded non-binding IA for futility based on the primary endpoint, the centrally read MD-CRS part II total score. Based on the results of the IA, the study may be stopped for futility.

During the conduct of the study, serious adverse events will be reviewed (Section 7.1.5), as they are reported from the investigational centers to identify safety concerns.

The study may be terminated by the sponsor for any reason at any time. For example, the sponsor should terminate the study in the event of the following:

- new toxicological or pharmacological findings or safety issues invalidate the earlier positive benefit-risk assessment
- discontinuation of the development of the IMP

If the study will be stopped, the patients who are terminated early will be followed according to Withdrawal Criteria and Procedures for the Patient (Section 4.3).

3.5. Schedule of Study Procedures and Assessments

Study procedures and assessments with their time points are presented in [Table 3](#). Detailed descriptions of each method of procedures and assessments are provided in [Section 6](#) (efficacy assessments), [Section 7](#) (safety assessments), and [Section 8](#) (pharmacokinetic and other assessments). Study procedures and assessments by visit are listed in [Appendix C](#).

For COVID-19 updates, refer to [Appendix M](#).

Table 3: Study Procedures and Assessments

	Screening	BL ^a	Titration							Maintenance			Follow-up		U
Study week ^b	-31 days	Day 1	1 (Day 7)	2 (Day 14)	3 (Day 21)	4 (Day 28)	5 (Day 35)	6 (Day 42)	7 (Day 49)	9 (Day 63)	12 (Day 84)	15 ^c / ET ^d (Day 105)	16/EOS (7 days from week 15 visit)	17 ^e (14 days from week 15 visit)	
Visit window (days)		0	+1	-1 and +3	±3 days from day 1/baseline and ≥5 days from last dose change							±2 days from week 15 visit			
In-clinic visit	X ^f	X			X				X	X	X	X	X		X
Telephone contact ^g			X	X		X	X	X						X	X ^h
Evaluate/adjust IMP ⁱ			X ^j	X ^j	X ^j	X ^j	X ^j	X ^j	X ^j						X
Informed consent/assent ^k	X														
Eligibility criteria	X	X													
Medical history and psychiatric history	X														
Demographics	X														
Vital signs and weight ^l	X	X ^m			X				X	X	X	X ^m	X		X
Physical examination	X	X										X			X ^h
Neurological examination	X	X										X			X ^h
Height	X											X			
12-lead ECG ⁿ	X				X				X			X	X ^o		X ^h
												X ^p			X ^q
Chemistry/hematology/urinalysis	X											X	X ^r		X ^h
Urine drug screen	X				X					X		X	X		X ^h
CYP2D6 genotype ^s	X														
β-HCG test ^t	X	X			X				X		X	X	X		X ^h

Clinical Study Protocol Amendment 05

	Screening	BL ^a	Titration							Maintenance			Follow-up		U
Study week ^b	-31 days	Day 1	1 (Day 7)	2 (Day 14)	3 (Day 21)	4 (Day 28)	5 (Day 35)	6 (Day 42)	7 (Day 49)	9 (Day 63)	12 (Day 84)	15 ^c / ET ^d (Day 105)	16/EOS (7 days from week 15 visit)	17 ^e (14 days from week 15 visit)	
Visit window (days)		0	+1	-1 and +3	±3 days from day 1/baseline and ≥5 days from last dose change							±2 days from week 15 visit			
Randomization		X													
MD-CRS part I (physician rated, with video recording) ^u		X								X	X	X	X		X ^h
MD-CRS part I (centrally read, with video review) ^u		X								X	X	X	X		X ^h
MD-CRS part II (physician rated, with video recording) ^u	X	X								X	X	X	X		X ^h
MD-CRS part II (centrally read, with video review) ^u	X (EAB)	X								X	X	X	X		X ^h
CaGI-I ^v					X				X	X	X	X	X		X ^h
CGI-I (global, physician rated) ^w			X	X	X	X	X	X	X	X	X	X	X		X ^h
CGI-S (global, physician rated)	X	X			X				X	X	X	X	X		X ^h
PEDI-CAT (ADL, caregiver completed, content-balanced version)		X										X			X ^h
PedsQL (QoL, patient/caregiver)		X										X			X ^h
PGI-I (global, patient/caregiver) ^y					X				X	X	X	X	X		X ^h
UHDRS-TMC (centrally read)		X								X	X	X			X ^h
UHDRS-TMD (centrally read)		X								X	X	X			X ^h
UHDRS-TMS (physician rated)		X								X	X	X			X ^h

Clinical Study Protocol Amendment 05

	Screening	BL ^a	Titration							Maintenance			Follow-up		U
Study week ^b	-31 days	Day 1	1 (Day 7)	2 (Day 14)	3 (Day 21)	4 (Day 28)	5 (Day 35)	6 (Day 42)	7 (Day 49)	9 (Day 63)	12 (Day 84)	15 ^c / ET ^d (Day 105)	16/EOS (7 days from week 15 visit)	17 ^e (14 days from week 15 visit)	
Visit window (days)		0	+1	-1 and +3	±3 days from day 1/baseline and ≥5 days from last dose change							±2 days from week 15 visit			
Children’s C-SSRS (Baseline/ Screening) ^x	X														
Children’s C-SSRS (Since Last Visit) ^x		X			X				X	X	X	X	X		X ^h
ESRS subscales I and II	X	X			X				X	X	X	X	X		X ^h
CBCL ^y	X	X			X				X	X	X	X	X		X ^h
ESS	X	X			X				X	X	X	X	X		X ^h
Dispense IMP		X ^z			X ^z				X ^{aa}	X ^{aa}	X ^{aa}				X ^h
Collect IMP					X				X	X	X	X			X ^h
Assess IMP accountability/ compliance/supply ^{bb}			X ^{cc}	X ^{cc}	X ^{dd}	X ^{cc}	X ^{cc}	X ^{cc}	X	X	X	X			X ^h
Assess adverse events		X	X	X	X	X	X	X	X	X	X	X	X	X	X
Concomitant medications	X	X ^{ee}	X ^{ee}	X ^{ee}	X ^{ee}	X ^{ee}	X ^{ee}	X ^{ee}	X ^{ee}	X ^{ee}	X ^{ee}	X ^{ee}	X ^{ee}	X ^{ee}	X ^{ee}
Contact RTSM	X				X				X	X	X	X			

^a The BL visit will occur (day 1), and the first dose of the IMP will be taken the next morning (day 2).
^b Assessment is to occur at the end of study week, unless stated otherwise.
^c The date and time of the last dose of study medication before the week 15 visit should be reported to the investigator/staff by the patient or caregiver. The investigational center will document the date and time of the sample collection.
^d For patients who withdraw prematurely, an ET visit should be conducted as soon as possible after the last dose of IMP. All patients who discontinue early will have a follow-up telephone contact for safety evaluation 2 weeks after ET visit; evaluations will be as described for week 17.
^e This visit is a telephone contact for safety evaluation, required only for patients who will not roll over into the open-label safety extension study for TV50717-CNS-30081.
^f The screening visit may be conducted over 2 separate visits at the discretion of the investigator.

Clinical Study Protocol Amendment 05

- ^g Telephone contacts at weeks 1, 2, 4, 5, and 6 will be conducted with non-recording live video. Telephone contact at week 17 is a phone contact only (ie, no live video streaming).
- ^h Assessment to be completed at investigator’s discretion.
- ⁱ Dose increases may not occur more frequently than every 5 days, except for patients ≥ 40 kg/88 lbs. For patients ≥ 40 kg/88 lbs, the first dose increase should be performed in an interval less than 5 days, only once, on day 3.
- ^j Dose adjustment will be made by the investigator after telephone contact with the patient and caregiver or in-clinic visit to evaluate dyskinesia reduction and adverse events. If the dose is escalated, the dose escalation will occur with the next morning’s dose.
- ^k [REDACTED]
- ^l Weight must be measured with shoes and outerwear off. Before pulse and BP are measured, the patient must be in a supine or semi-erect/seated position and resting for at least 3 minutes (the same position and arm or leg should be used each time vital signs are measured for a given patient).
- ^m Orthostatic BP and pulse will be measured after the patient is in a standing position for at least 3 minutes (for patients who are able to stand); for patients who find standing difficult or do not allow for a reliable BP and pulse measurement, alternative methods to collect orthostatic BP and pulse should be discussed with the medical monitor.
- ⁿ All ECGs will be performed after at least 5 minutes rest in a supine or semi-supine position.
- ^o Perform ECG if there was a significant abnormality at the ET visit.
- ^p [REDACTED]
- ^q [REDACTED]
- ^r Patients with clinically significant laboratory abnormalities at week 15 will have those laboratory evaluations repeated at the week 16 visit.
- ^s The patient’s CYP2D6 genotype results will be provided to the RTSM, which drives each patient’s dose regimen, and the patient’s CYP2D6 genotype will remain blinded during the conduct of the study.
- ^t For females who are postmenarchal or aged ≥ 12 years of childbearing potential. Serum test will be administered at screening and week 15, whereas a urine test will be administered at baseline and all other in-clinic visits where this test is administered.
- ^u MD-CRS parts I and II assessments are done locally at the investigational center, by the investigator, and video recorded. An EAB will confirm, at the screening visit, that choreiform movement disorder is the predominant dyskinetic movement disorder and that DCP severity represented by an MD-CRS part II score is ≥ 10 . The EAB will inform the local rater if their assessment is different than the local rater’s assessment; however, it is the investigator who determines the subject’s eligibility. All the subsequent MD-CRS ratings will be performed by the investigator and video recorded and then centrally read, in a blinded manner.
- ^v CaGI-I and PGI-I are to be completed before all other investigator-rated scales during visits where CaGI-I and PGI-I are collected.
- ^w During telephone contact, the CGI-I scale can only be done if non-recording video is available, allowing the investigator to complete the required assessment.
- ^x The children’s C-SSRS questionnaire will be presented to patients who have reached ≥ 12 years of age at screening or 11 years of age at screening but will turn 12 years of age during the study. Children 13 years of age and under must be interviewed in conjunction with the caregiver. For children over 13 years of age, parent/legally accepted representative involvement is strongly encouraged. Questions should be directed to the child, but the parent/legally accepted representative should be encouraged to add relevant information.
- ^y A full CBCL assessment (Competence Scale [Parts I to VII] and a Syndrome Scale [behavioral items]) will be performed at screening and week 15/ET. The Syndrome Scale part of the CBCL assessment only will be performed at baseline and weeks 3, 7, 9, 12, and 16/EOS.

Clinical Study Protocol Amendment 05

- ^z IMP will be dispensed in the clinic. At the baseline visit, patients will receive IMP kits of increasing doses sufficient for 3 weeks. At the week 3 visit, 4 additional kits of increasing doses will be dispensed to cover the following 4 weeks until the end of the titration period at week 7. These supplies will allow the patient to maintain their titration scheme between clinic visits by way of remote caregiver/patient telephone contacts. Dose adjustments can be made up to and including the week 7 in-clinic visit. If an optimal dose is reached before then, the dose of IMP should not be increased any further, but the patient should continue on that same dose for the remainder of the titration period and throughout maintenance dosing. The investigational center will determine titration (ie, starting the next dose) for the patient by telephone. See [Table 4](#) for baseline weight-based dosing titration. For any dose adjustment, the investigator or designee should confirm that patients have the bottle that contains the appropriate tablet strength and quantity to complete the recommended daily regimen.
- ^{aa} Patients will receive doses for 3 weeks (± 3 days) of maintenance treatment.
- ^{bb} Study drug accountability will be assessed during in-clinic visits only. A check for compliance with TEV-50717 intake will be performed during each in-clinic visit and telephone contact after TEV-50717 has been dispensed.
- ^{cc} The study staff needs to discuss the drug status during the telephone contacts to ensure that the patients have adequate tablets, inform the patients if they should titrate, and remind them to bring used and unused IMP bottles to the next in-clinic visit.
- ^{dd} During the week 3 visit, the investigator or designee will make sure the patient receives the last treatment kit back so the patient can take the evening dose to complete the week 3 dosing for that day. Refer to the pharmacy manual for further details.
- ^{ee} Caregivers and patients will be instructed during the course of the study to notify the investigator if any new medication is prescribed/administered (other than TEV-50717) or if there is any change in current medications, including over-the-counter medications. Any new and/or any change in current medications should be reviewed with the investigator.
- β -HCG=beta human chorionic gonadotropin; ADL=activities of daily living; BL=baseline visit; BP=blood pressure; CaGI-I=Caregiver Global Impression of Improvement; CBCL=Child Behavior Checklist (for ages 6-18); CGI-I=Clinical Global Impression of Improvement; CGI-S=Clinical Global Impression of Severity; C-SSRS=Columbia-Suicide Severity Rating Scale; CYP2D6=cytochrome P450 2D6; DCP=dyskinesia in cerebral palsy; EAB=Enrollment Adjudication Board; ECG=electrocardiogram; EOS=end of study visit; ESRS=Extrapyramidal Symptom Rating Scale (subscales I and II); ESS =Epworth Sleepiness Scale (for children and adolescents); ET=early termination visit; [REDACTED]; IMP=investigational medicinal product; MD-CRS=Movement Disorder-Childhood Rating Scale; PEDI-CAT=Pediatric Evaluation Disability Inventory-Computer Adapted Test; PedsQL=Pediatric Quality of Life Inventory; PGI-I=Patient Global Impression of Improvement; [REDACTED]; QoL=quality of life; RTSM=Randomization and Trial Supply Management; U=unscheduled visit; UHDRS-TMC=Unified Huntington’s Disease Rating Scale-Total Maximal Chorea; UHDRS-TMD=Unified Huntington’s Disease Rating Scale-Total Maximal Dystonia; UHDRS-TMS=Unified Huntington’s Disease Rating Scale-Total Motor Score.

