Dose adjustments can be made up to and including the week 7 in-clinic visit. If an optimal dose is reached before the week 7 in-clinic visit, the dose of IMP should not be increased further, but the patient should continue on that dose for the remainder of the titration period and throughout the maintenance period. If a patient experiences a “clinically significant” adverse event attributable to the IMP, the investigator will first determine if a dose reduction (to the previous dose level) or suspension is necessary and possible. If the determination that a patient requires a dose reduction or suspension is made during a telephone contact, an unscheduled clinic visit should be conducted as soon as practicable thereafter.

Maintenance period (8 weeks): Patients will continue to receive their maintenance dose over the next 8 weeks, although a 1-time dose reduction (to the previous dose level for the remainder of the study) for adverse events is allowed. Patients will return to the clinic at weeks 9, 12, and 15 for assessments of efficacy and safety.

Washout period and follow-up: All patients will discontinue IMP at the week 15 visit and will return 1 week later for the end-of-study (EOS) visit. Patients who complete the study may be eligible to begin participation in the open-label safety extension Study TV50717-CNS-30081 at that time. At the week 16 visit, patients may choose to enter Study TV50717-CNS-30081 (on

that day) or up to 1 week later (2 weeks from the week 15 visit). Patients who complete treatment but choose not to participate in the open-label safety extension Study TV50717-CNS-30081 any time before week 17 of Study TV50717-CNS-30080 will be contacted for a safety evaluation call occurring 2 weeks after their last dose of IMP. Additional details for patients to enter Study TV50717-CNS-30081 are provided in the TV50717-CNS-30081 protocol.

When approximately 50 patients have completed the study (including follow-up), an independent Data Monitoring Committee (iDMC) will perform an unblinded non-binding interim analysis (IA) for futility based on centrally read MD-CRS part II total score.

An iDMC charter will be developed for the IA, and the procedures to ensure the integrity of the study will be provided in the charter.

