5.4. Treatment after the End of the Study

All patients will discontinue IMP at the week 15 visit and will return 1 week later for the EOS visit.

Patients will not receive the evening IMP dose on this day.

Patients who complete the study may be eligible to begin participation in the open-label safety extension Study TV50717-CNS-30081. At the week 16 visit, patients may choose to enter Study TV50717-CNS-30081 (on that day) or up to 1 week later (2 weeks from the week 15 visit). Patients who complete treatment but choose not to participate in the open-label safety extension Study TV50717-CNS-30081 before week 17 of Study TV50717-CNS-30080 will be contacted for a safety evaluation call occurring 2 weeks after their last dose of IMP. Additional details for patients to enter Study TV50717-CNS-30081 are provided in the TV50717-CNS-30081 protocol.

Note: Patients can also roll over to the extension study within 2 to 4 weeks after the week 15 visit but will be required to complete additional scales and tests as part of Study TV50717-CNS-30081.

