7.1.2. Recording and Reporting of Adverse Events

For recording of adverse events, the study period is defined for each patient as the time period from signature of the ICF to the end of the follow-up period. The follow-up period of recording of adverse events is defined as 2 weeks after the last dose of IMP or up to baseline/day 1 in the open-label extension Study TV50717-CNS-30081 (whichever comes first) or 2 weeks after the ET visit for patients who terminate early from the study.

All adverse events that occur during the defined study period must be recorded both on the source documentation and the CRF, regardless of the severity of the event or judged relationship to the IMP. For serious adverse events, the serious adverse event form must be completed, and the serious adverse event must be reported immediately (Section 7.1.5.3.1). The investigator does not need to actively monitor patients for adverse events after the defined periods.

At each contact with the patient, the investigator or designee must question the patient and/or parent(s)/caregiver (as applicable) about adverse events by asking an open-ended question such as “Have you had any unusual symptoms or medical problems since the last visit? If yes, please describe.” All reported or observed signs and symptoms will be recorded individually, except when considered manifestations of a medical condition or disease state. A precise diagnosis will be recorded whenever possible. When such a diagnosis is made, all related signs, symptoms, and any test findings will be recorded collectively as a single diagnosis on the CRF and, if it is a serious adverse event, on the serious adverse event form.

The clinical course of each adverse event will be monitored at suitable intervals until resolved, stabilized, or returned to baseline; until the patient is referred for continued care to a health care professional; or until a determination of a cause unrelated to the IMP or study procedure is made. Adverse events of patients rolling over to the open-label extension Study TV50717-CNS-30081 will continue to be monitored as part of the open-label extension study.

To enable the assessment of the potential relationship of an adverse event and plasma concentration of IMP and metabolites, blood samples will be collected based on the scenarios described in [Table 9](#).

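### Table 3 footnote e exempts late entrants to the extension from the week 17 safety call that the synopsis and Sections 3.1 and 5.4 require

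*Protocol*

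**What the plan says.** Several places in the protocol decide who receives the week 17 call.

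- **Section 3.5, Table 3, footnote e:** the call is "required only for patients who will not roll over into the open-label safety extension study". No time limit is attached to rolling over.
- **Section 5.4:** completers who choose not to take part in the extension "before week 17 of Study TV50717-CNS-30080 will be contacted for a safety evaluation call occurring 2 weeks after their last dose of IMP". Section 3.1 and two places in the synopsis (general study design; care after participation) carry the same rule, worded as "any time before week 17 of Study TV50717-CNS-30080 will be contacted for a safety evaluation call".
- **Section 5.4, note:** "Patients can also roll over to the extension study within 2 to 4 weeks after the week 15 visit". These patients "will be required to complete additional scales and tests as part of Study TV50717-CNS-30081".
- **Appendix C, item 5b:** lists the telephone contact, adverse events and concomitant medications at 2 weeks ±2 days from week 15, and says nothing of a rollover exemption.
- **Table 3, footnote d:** early terminators have a separate call, timed from their termination visit.

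Two further provisions set the timing. Section 5.4 fixes the last dose: "All patients will discontinue IMP at the week 15 visit and will return 1 week later for the EOS visit". Section 7.1.2 defines the adverse event follow-up period for completers as "defined as 2 weeks after the last dose of IMP or up to baseline/day 1 in the open-label extension Study TV50717-CNS-30081 (whichever comes first").

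**The concern.** The word *only* makes footnote e an exclusion, not a shortened statement of the rule in the body. A completer who enters the extension in week 18 or 19 is to be called under Section 5.4 and is exempt under the schedule table. A site that follows either text departs from the other.

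The footnote is also hard to apply on the day. The call falls about 14 days after the last dose, while entry is possible until day 28, so staff would have to predict whether an undecided family will enter later. The rule in the body turns on something known at the time: whether the patient has entered yet.

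At stake is a planned safety contact in children and adolescents shortly after the drug is stopped. No efficacy analysis depends on it.

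**Working it through.** **Who is called under each rule.** Take the week 15 visit, the day of the last dose, as day 0.

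| Patient | Footnote e | Synopsis, 3.1, 5.4 |
|---|---|---|
| Completer, enters before week 17 | no call | no call |
| Completer, enters after day 14 and up to day 28 | no call | call |
| Completer, never enters | call | call |
| Early terminator | call under footnote d | call 2 weeks after termination visit (3.1) |

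Only the second row differs.

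**Inputs for timing.**
- Week 16 visit: day 7 ±2, so days 5 to 9 (Table 3, Appendix C).
- Week 17 call: day 14 ±2, so days 12 to 16 (same sources).
- Late entry: days 15 to 28 (Section 5.4 note; day 14 is the end of the standard entry window).
- End of adverse event period for a late entrant: day 14, because 2 weeks after the last dose comes before extension day 1 (Section 7.1.2).

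**Part of the window not yet asked about if the call is skipped** = 14 minus the day of the week 16 visit.
- Nominal: 14 - 7 = 7 days.
- Range: 14 - 9 = 5 to 14 - 5 = 9 days.

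**Delay of inquiry** = day of entry minus day of call.
- Call on day 14: 15 - 14 = 1 day to 28 - 14 = 14 days.
- Call on days 12 to 16: 15 - 16 = -1 day to 28 - 12 = 16 days.

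A negative value means that entry comes before a permitted late call, so nothing is delayed. A call on day 12 or 13 would itself leave the last day or two of the window unasked, so the call closes the window exactly only at its nominal date or later.

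**Longest interval between planned contacts, entry on day 28.**
- With the call: 28 - 14 = 14 days (28 - 16 = 12 to 28 - 12 = 16).
- Without it: 28 - 7 = 21 days (28 - 9 = 19 to 28 - 5 = 23).

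The number of late entrants is not given, so no patient count can be derived.

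**The case against.** **The timing phrase may date the choice, not the entry.** On that reading a completer who already intends to enter late has not chosen against the extension, neither rule asks for a call, and there is no conflict. The wording permits this, but it is strained. The sentence just before it in Sections 3.1 and 5.4 sets a window for entry (week 16, or up to a week later), so the limit most naturally refers to entry. Under the other reading the site would still have to act at day 14 on an event that may happen at day 28.

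**Footnote e may mean the standard path only.** Late entry appears only as a note in Section 5.4, and Appendix C lists the call without exemption. A site that reads the whole protocol would probably make the call. This lowers the chance of harm. It does not reconcile the footnote, which is current text in the table sites work from and says *only*.

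**Safety is covered elsewhere.** This largely stands. Every completer has a planned clinic visit at week 16 with adverse event inquiry and the safety scales. Unscheduled visits are available. Families are told to report changes in mood or behavior at once (Sections 7.9 and 7.10). Serious events that come to the investigator's notice after follow-up remain reportable (Section 7.1.5). Section 7.1.2 adds: "Adverse events of patients rolling over to the open-label extension Study TV50717-CNS-30081 will continue to be monitored" in that study.

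A reader might infer that late entrants are lost to safety follow-up, or that their events in the second week off drug go unrecorded. The documents do not support this: those patients have a later planned encounter and continued monitoring. Nor does the conflict reach early terminators, who have their own call.

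**Conclusion.** The conflict is real and narrow. Footnote e, taken literally, drops a contact that the synopsis and Sections 3.1 and 5.4 require, and it does so only for completers who enter the extension after week 17 and within 4 weeks of week 15.

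For them, inquiry about roughly the last 7 days (5 to 9) of the 14-day window is put off to extension entry, by 1 to 14 days nominally or about -1 to 16 days with the call window. This rests on two assumptions: that the timing phrase in the body refers to entry, and that adverse events are asked about when the patient enters the extension. Sections 5.4 and 7.1.2 point to the second, but the extension protocol is not available here.

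The consequence is minor: delayed inquiry in a subgroup of unknown size, with no bearing on efficacy. It is worth correcting because the two instructions cannot both be followed for these patients.

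**What to change.** Reword footnote e along these lines: *required for patients who complete treatment and have not entered Study TV50717-CNS-30081 by the time of the week 17 contact, including those who plan to enter later; for patients who terminate early see footnote d.*

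Tying the rule to the time of the contact matters. Standard entry runs to 2 weeks after week 15, which is week 17 itself. A rule worded as entry before week 17 would call a day-14 entrant on extension day 1, when the adverse event period has already ended. Limiting the text to completers keeps early terminators under footnote d, where the call is timed from their termination visit.

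The cost is one footnote. No procedure is added, because the body of the protocol already requires the call.
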